8.1. Drugs (trade and generic, dosage, route of administration)

N/A

8.2. Devices

All health devices, including fitness tracker and wireless BP monitor will be provided to each participant by the study team.

8.3. Biologics

N/A

8.4. Laboratory Tests

Blood test:

A total 4.0ml of peripheral blood will be drawn into two EDTA tube during pre-test. The EDTA tube will be centrifuged at 4,000 rpm +4°C for 10 minutes, then serum will be transferred into an Eppendorf tube and stored at -80°C. The Illumina Infinium system will be used for high-throughput genotyping of single nucleotide polymorphisms (SNPs) using microarrays. Genotyping will be conducted by Biobanking and Genome Analysis Core Laboratory Center.

Urine test:

Each participant will be asked to complete two 24-hour urine collections at baseline and 8-week and the containers and instructions for 24-hour urine collection will be given to participants at the baseline visit. The PI will visit the participant's home to pick up the urine sample at their convenience by following general precautions such as wearing a face mask and social distancing.

[name] for Renal Precision Medicine lab specializes in metabolomics analysis and will use the targeted capillary electrophoresis/mass spectrometry (CE/MS) method for 48 amino metabolites using the 24-hour urinary sample.

Sodium, 24-hour urine with creatinine will be assessed using the 10 mL urine aliquot. The urinary sample will be sent to Quest Diagnostics.

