12.2. Sample Size Determination

Include number of participants to recruit, screen, and enroll to have adequate power to test the key hypotheses for the study. Provide all information needed to validate your calculations and judge the feasibility of enrolling and following the necessary number of participants.

Given the pilot nature of the study, we will recruit 40 participants and conduct a stratified randomized clinical trial. Specifically, 40 subjects will be recruited, and block randomized to either an intervention or a control group in a 1:1 ratio. Per power analysis, the study will be underpowered; therefore, quantitative outcomes will be interpreted only as feasibility and pilot data. A sample size of 40 subjects will give us adequate sample size to provide meaningful confidence intervals for our estimates of feasibility and preliminary effects. With this overall sample size, we expect to have sufficient diversity of input on the intervention components to plan refinements prior to testing in a larger intervention trial.

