12.4. Statistical Analyses

Include analysis of primary efficacy endpoints, secondary endpoints, safety analyses, and any planned interim analyses

Data analysis will be performed with SAS (Cary, NC) version 9.4 and R (Vienna, Austria) version and 3.6+. After verifying the normality of distribution of the continuous variables, the mean and standard deviations will be calculated. If data are not normally distributed, log transformation will be conducted. All analyses will also be conducted after controlling for age, gender, and BMI.

Specific Aim 1: Using pre-test data, random forest will be applied to identify associations between 48 amino metabolites, BP phenotypes (including SBP or DBP), and 24-hour urinary excretion to predict the classification of study subjects and will be achieved by R program. For urinary metabolites nominated by the random forest analysis, generalized linear model (GLM) will further be performed to generate p values and false discovery rates (FDR) to correct for testing multiple urinary metabolites using the Benjamini-Hochberg procedure.

Specific Aim 2a: Using both pre and post-test data, feasibility will be assessed by measuring: 1) % subjects who come to the 8-week follow-up; 2) number of education sessions attended online (intervention group); 3) % days that subject log his/her meals using mobile dietary app; and, 4) % days that subject log in-home BP using BP monitor device. The preliminary effect of SRD on the outcome variables will be tested by using a repeated measures analysis of variance (RM-ANOVA) with one between-subjects factor (intervention and control) and one within-subject factor (pre-test and post-test).

Specific Aim 2b: We estimate that 20 participants/group will provide sufficient data for estimating intervention effects on metabolomic profiling and reduction of urinary sodium level and BP. The estimated effect size will be used for sample size justification and power analysis for a future larger study.

Specific Aim 3: Using pre-test data, analysis of targeted genotyping will be conducted by the R program. A moderator analysis will be used to determine whether the relationship between urine metabolites or sodium intake and BP depends on the SS candidate gene (GNAI2 SNPs).

All testing will be two-sided and p<0.05 or FDR < 10% will be considered as significant.

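### If Aim 1 analyses metabolites as 24-hour amounts, incomplete urine collections can produce false metabolite-sodium associations, and the plan makes no use of the creatinine it assays

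*Combined protocol and SAP*

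**What the plan says.** Section 8.4 describes the urine work. "Each participant will be asked to complete two 24-hour urine collections at baseline and 8-week"; the containers and instructions are handed out at the baseline visit, and the sample is picked up from the participant's home. The metabolomics laboratory uses a capillary electrophoresis/mass spectrometry "method for 48 amino metabolites using the 24-hour urinary sample". For the other assay, "Sodium, 24-hour urine with creatinine will be assessed using the 10 mL urine aliquot". That both aliquots come from the same container is the natural reading, but it is not stated outright.

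Section 12.4, Specific Aim 1, works on pre-test data: "random forest will be applied to identify associations between 48 amino metabolites, BP phenotypes (including SBP or DBP), and 24-hour urinary excretion". Sections 2 and 3.1 make clear that the excretion in question is sodium. Metabolites nominated by the random forest go on to a generalized linear model, with false discovery rates "to correct for testing multiple urinary metabolites using the Benjamini-Hochberg procedure". On adjustment: "All analyses will also be conducted after controlling for age, gender, and BMI". On significance: "All testing will be two-sided and p<0.05 or FDR < 10% will be considered as significant".

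Creatinine is not mentioned again after Section 8.4. The analysis population in Section 12.3 is defined by having the measurements, with no condition on whether a urine collection was valid. No section gives a volume limit, a question on missed voids, a completeness criterion or a normalisation. No section says whether metabolites are analysed as concentrations, 24-hour amounts or ratios.

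**The concern.** A 24-hour amount is a concentration multiplied by the collected volume. When a participant misses a void, the recorded amounts of sodium and of every metabolite fall by roughly the same factor. Over-collection does the reverse. Across participants this shared factor makes sodium and metabolites correlate even where no biological relation exists.

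The planned safeguards do not address it. Age, gender and BMI do not measure missed voids. Benjamini-Hochberg controls the consequences of testing many hypotheses, but a correlation caused by shared measurement error is really present in the data and passes through. The random forest step would tend to nominate affected metabolites rather than screen them out.

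What is at stake is the list of metabolites reported as markers of sodium, which Section 2 presents as groundwork for later personalised nutrition interventions. Incomplete collection also adds noise to urinary sodium, the outcome of Hypothesis 1, and to the effect size that Aim 2b is meant to supply for a larger trial.

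**Working it through.** The plan states no figure on this point, so there is nothing to reproduce.

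**Inputs from the documents.** n = 40 (Section 12.2); 48 metabolites (8.4); three covariates, two-sided 0.05, FDR 10% (12.4). Section 12.3 restricts the analysis to completers, so 40 is an upper limit.

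**Assumptions, not in the documents.** Metabolites are analysed as log 24-hour amounts. True sodium and true metabolite excretion are independent. The biological CV is 40% for sodium and 40% (alternatively 70%) for metabolites. The completeness CV is 10%, 20% or 25%. Creatinine has a CV of its own of 15% or 25% after covariates.

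**Step 1: induced correlation.** On the log scale, variance = ln(1 + CV²). With v for completeness, s for sodium and m for the metabolite,

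r = v / √[(s + v)(m + v)].

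For 20% completeness and 40% biological CVs: v = ln(1.04) = 0.0392 and s = m = ln(1.16) = 0.1484, so r = 0.0392 / 0.1876 = 0.209.

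**Step 2: false-positive rate per metabolite.** By Fisher's z with three covariates, the shift is atanh(r) × √(40 − 3 − 3). Here it is 0.2121 × 5.831 = 1.237. The rate is P(Z > 1.96 − 1.237) + P(Z < −1.96 − 1.237) = 0.235 + 0.001 = 0.236, against a nominal 0.05.

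**Step 3: with log creatinine as a fourth covariate.** Creatinine carries the same completeness factor plus its own variance k. The completeness variance left after adjustment is vk/(v + k). For a 15% creatinine CV, k = ln(1.0225) = 0.0223, which leaves 0.0142. Then r = 0.0142 / 0.1626 = 0.087, the shift is 0.0875 × √33 = 0.503, and the rate is 0.079.

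| Completeness CV | Metabolite CV | Induced r | Rate, age/gender/BMI only | Plus log creatinine (CV 15%) | Plus log creatinine (CV 25%) |
|---|---|---|---|---|---|
| 10% | 40% | 0.06 | 6.6% | 5.7% | 6.1% |
| 20% | 40% | 0.21 | 23.6% | 7.9% | 12.6% |
| 20% | 70% | 0.14 | 12.6% | 6.1% | 8.0% |
| 25% | 40% | 0.29 | 41.3% | 8.8% | 16.6% |

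Simulation of the same model agrees within about one percentage point (for example 24% and 42% for the 20% and 25% rows with 40% metabolite CV).

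**Step 4: after Benjamini-Hochberg at 10%.** This was simulated with all 48 metabolites null. With complete collections, the chance of at least one discovery is about 10%. At 20% completeness CV and 40% biological CVs it is 65–67%, with a median of 2 to 3 false discoveries and a mean of 6.5. With creatinine added it falls to about 22% (creatinine CV 15%) or 39% (25%). The random forest pre-selection was not simulated.

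**Step 5: a different error model.** Suppose instead that 20–50% of participants under-collect, recovering between 40–50% and 95% of the day's urine, with sodium CV 35–45% and metabolite CV 35–70%. The per-metabolite rate is then 8–69%. In a middle case (30% under-collecting, recovering as little as 50%; CVs 35% and 50%) it is 18%, with a 56% chance of at least one discovery. Adding creatinine brings these to 7% and 19%.

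**Step 6: if metabolites are concentrations.** With 24-hour sodium on the other side, missed voids assumed not to change concentration and volume independent of sodium, r is about 0 and the rate about 5%. The artefact disappears.

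**Step 7: dividing both measures by creatinine.** Completeness cancels, but creatinine's own variance k becomes a shared denominator: r = k/(s + k). At a 15% CV, r = 0.0223 / 0.1707 = 0.130 and the rate is 12%, even when every collection is complete. At 25%, k = 0.0606, r = 0.290 and the rate is about 41–42%, worse than the uncorrected 24% at 20% completeness CV.

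**The case against.** A reader might infer that Aim 1 will report false sodium markers. The documents do not support that. The artefact needs both material incompleteness and metabolites analysed as 24-hour amounts, and neither is established. If metabolites are concentrations against 24-hour sodium, Step 6 shows no inflation. This objection stands, and it is why the point is conditional.

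A reader might also multiply 24% by 48 and expect 11 or 12 false markers. That count applies unadjusted p-values to every metabolite. The plan tests only nominated metabolites and applies Benjamini-Hochberg, and Step 4 gives a median of 2 to 3. The significance sentence in Section 12.4 joins the two criteria with an or, so the unadjusted rule is not wholly excluded, but it should not set the headline.

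The size depends on assumed CVs. At 10% completeness CV the rate is close to nominal, and a 70% metabolite CV halves the inflated figure at 20%. This stands too.

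Section 12.2 limits quantitative results to a feasibility and pilot reading, which lowers the consequence. It does not remove it, because Section 12.4 still declares significance and the metabolite profile is an aim in its own right. Metabolite-BP associations are not affected by the shared error. In Aim 2, completeness error unrelated to arm adds noise but does not bias the randomised comparison.

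Finally, the instructions given to participants and the attached Schedule of Activities were not available, so recording of volume or missed voids cannot be ruled out. Even if they are recorded, the analysis section makes no use of them.

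**Conclusion.** The point holds in conditional form. It is firm that metabolites and sodium both come from 24-hour urine collected at home, that creatinine is assayed, and that no analysis, exclusion or normalisation uses it. If 24-hour amounts are analysed and some collections are incomplete, metabolite-sodium associations are biased upward in a way that neither the listed covariates nor Benjamini-Hochberg corrects.

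The size rests wholly on assumed CVs. With 40% biological CVs and n = 40, the per-metabolite false-positive rate runs from about 7% to 42% as the completeness CV goes from 10% to 25%, and it is about 24% at 20% (about 13% if the metabolite CV is 70%). The stronger readings, that false associations are certain or that about a quarter of the panel would be reported, are not supported. The change is worth making before analysis because the plan leaves the scale open and already pays for the measurement that would reduce the problem.

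**What to change.** 1. State in Section 12.4 the scale on which metabolites enter Aim 1. If concentrations are used for both metabolites and sodium, urine dilution becomes the shared error and needs its own handling.
2. If 24-hour amounts are used, add log 24-hour creatinine excretion to age, gender and BMI in the Aim 1 metabolite-sodium models.
3. Record total volume and reported missed voids, and pre-specify a creatinine-based completeness flag. Repeat Aims 1 and 2 without flagged collections as a sensitivity analysis.
4. Do not divide both sodium and metabolites by creatinine (Step 7).
5. Clarify whether there are two collections in all or two per visit, and confirm that both aliquots come from the same container.

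The cost is one degree of freedom and one sensitivity analysis on a value already assayed. Creatinine is a noisy marker of completeness, so some bias remains: about 8% false positives at 20% completeness CV if its own CV is 15%, and about 13% if it is 25%. Where a metabolite is itself related to creatinine, the adjustment will also remove some true signal, so results with and without it should both be shown.

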8.5. Imaging Procedures

N/A

8.6. Other Research Procedures (e.g., other safety and efficacy assessments.)

Digital self-monitoring for diet and in-home monitoring of BP will be recorded automatically via wearable fitness tracker and wireless BP monitor over 8 weeks. The following data will be collected by self-reported questionnaire or relevant health equipment. Informed consent will be obtained either at pre-study visit (Day -1) or baseline visit (Day 1).

- Individual characteristics (baseline): We will collect demographic information such as age and gender.
- Physical Assessment (baseline and 8-week): Height, weight, and blood pressure will be measured at baseline and 8-week.

8.7 Attach a Schedule of Activities (SOA) Excel File [Download the Template here: [Schedule of Activities](#)]

Check to indicate that the SOA Excel File is attached →

9. Preparation/Handling/ Storage/Accountability of Investigational Drug, Biologic, or Device

N/A - This study does not include any investigational products (e.g. drugs, devices or biologics)

N/A - An Investigator Brochure is attached

N/A - A Drug/Device Manual is attached

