		1.1. Revision Date(s) add rows as needed	

Study Title: Examining the individual response to a restricted sodium diet in hypertensive patients

2. Background

Briefly discuss the important literature relevant to the trial and that provides background for the trial. Include the importance of the trial and any relevant treatment issues or controversies.

Excessive dietary sodium intake is an independent risk factor of hypertension and cardiovascular disease. A vast array of efforts have tried to reduce sodium consumption based on evidence indicating a public health benefit. Yet this benefit has been questioned, mainly based on studies showing variability in individual responses to a sodium-restricted diet (SRD).

The original Sodium Watchers Program (R01NR012967) was developed and implemented by [name] (University of Kentucky). In this pilot study, the modified Sodium Watchers Program will propose improving adherence to an SRD through education and digital self-monitoring for gradual reduction to low salt foods.

This variability may result from a range of factors, from genetics and lifestyle to various environmental parameters. The response of BP regulation to dietary interventions has been investigated through a metabolomics approach in several studies where different dietary patterns were adopted, including the Dietary Approaches to Stop Hypertension (DASH), Optimal Macronutrient Intake Trial for Heart Health Diets, and use of the Mediterranean Diet. BP was significantly associated with 6-10 urinary metabolites reflecting dietary intake. These results demonstrate, in a trial setting, changes in metabolite profile from manipulation of dietary macronutrient content to lower BP levels. However, the metabolite profile in relation to micronutrients such as dietary sodium intake remains unknown.

The study aims are (1) to examine the associations of urine metabolites with urinary sodium levels and BP control; (2a) to determine the feasibility and preliminary efficacy of delivering an SRD intervention focused on changes in metabolomic profiling and reduction of urinary sodium level and BP; (2b) to estimate the effect size of the SRD intervention on metabolomic profiling, urinary sodium level, and BP metrics and (3) to examine the association of the SS candidate gene with urine metabolites, sodium excretion, and BP control.

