5.2. Overall Design Select all applicable												
	Randomization				Cluster Randomized							
	Group-Sequential				Adaptive Design							
	Parallel Design				Placebo-Controlled							
	Superiority				Equivalence		 Non-inferiority					
Device		Pilot			Pivotal		 Post-Approval					
Drug/Biologic		Phase 1		Phase 1/2		Phase 2		Phase 2/3		Phase 3		Phase 4
	Dose escalation		If yes, details →									
	Dose ranging		If yes, details →									
	Sub-studies		If yes, details →									

5.3. Other Design Details: This will be an 8-week randomized controlled trial. The study will start after the IRB approval from UT Health San Antonio. Subjects recruitment will be performed in the communities and utilized EHR (Electronic Health Record) and data collection will be conducted at UT Health San Antonio School of Nursing. Bio-specimen (blood sample) will be transported to and processed in the laboratories of Center for Renal Precision Medicine and School of Nursing at UTHSCSA.

6. Study Population

6.1. Study Population(s) Label/Name	6.2. Identify the criteria for inclusion The criteria that every potential participant must satisfy, to qualify for study entry.	6.3. Identify the criteria for exclusion The characteristics that make an individual ineligible for study participation.
To add more populations – select a row, copy & paste	All individuals in this study population must meet all of the inclusion criteria in order to be eligible to participate in the study	All individuals in this study population meeting any of the exclusion criteria at baseline will be excluded from study participation.

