10.3. Permitted Concomitant Therapy

This section should be consistent with the medication restrictions in the inclusion/exclusion criteria previously listed. Describe how allowed concomitant therapy might affect the outcome (e.g., drug-drug interaction, direct effects on the study endpoints).

Participants in both groups won't be restricted from their previous antihypertensive medications. All relevant data, including medication usage and other forms of therapy, will be considered when conducting data analysis wherever necessary to avoid or minimize its effects on study endpoints.

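### Aim 3 compares genotypes at baseline with no ancestry covariate, so ancestry differences can appear as direct GNAI2 associations and, under a further condition, as moderation

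*Combined protocol and SAP*

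**What the plan says.** The covariate rule in section 12.4 applies to every aim: "All analyses will also be conducted after controlling for age, gender, and BMI". The Aim 3 paragraph adds no covariate. It states "Using pre-test data, analysis of targeted genotyping will be conducted by the R program", and then plans a moderator analysis of "whether the relationship between urine metabolites or sodium intake and BP depends on the SS candidate gene (GNAI2 SNPs").

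The aim in section 2 (Background) is wider: "to examine the association of the SS candidate gene with urine metabolites, sodium excretion, and BP control". The objectives table in section 3 repeats it. Direct gene associations are thus an aim, but section 12.4 writes out only the moderator model.

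On data sources, section 8.6 says "We will collect demographic information such as age and gender". Section 8.4 says "The Illumina Infinium system will be used for high-throughput genotyping of single nucleotide polymorphisms (SNPs) using microarrays", with no mention of using the array for ancestry components. Section 5.3 says "Subjects recruitment will be performed in the communities and utilized EHR (Electronic Health Record"), and the criteria in section 6 do not limit ancestry. The only other adjustment language is in section 10.3: "All relevant data, including medication usage and other forms of therapy, will be considered when conducting data analysis wherever necessary".

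**The concern.** Randomization protects comparisons between arms. Aim 3 compares genotype groups at baseline, so it is an observational association study within the trial sample. Ancestry can be a common cause of allele frequency on one side and of diet, urine composition and BP on the other. Where it is, a SNP with no effect will correlate with the outcome, and adjusting for age, gender and BMI does not close that path. Controlling the false discovery rate does not help either, because it deals with multiplicity and not with bias.

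What is at stake is a misleading exploratory lead. Section 12.4 still calls a result significant at p<0.05 or FDR below 10%, and section 2 says that the findings will be a foundation for personalized nutrition work.

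**Working it through.** The plan has no figure of its own to reproduce: it gives no allele frequency, ancestry mix or effect size for Aim 3.

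**Inputs from the documents.** N = 40 (section 12.2); two-sided 0.05 (section 12.4); three covariates (section 12.4).

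**Assumed inputs.** Two ancestry groups of equal size; allele frequencies p1 and p2; an outcome gap of d within-group SDs; additive allele count G; no true gene effect.

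**Direct association, by formula.** Let A be the 0/1 ancestry indicator, with variance 0.25.
- Cov(A,G) = 0.25 × 2(p2 − p1) = 0.5(p2 − p1)
- Var(G) = average of 2p(1 − p) over the two groups + (p2 − p1)²
- Bias per allele = d × Cov(A,G) / Var(G)
- r² = Cov(A,G)² / (0.25 × Var(G)); residual variance = 1 + 0.25d²(1 − r²)
- SE = √(residual variance / (40 × Var(G))); λ = bias / SE
- Type I error ≈ P(Z > 1.96 − λ) + P(Z < −1.96 − λ)

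Example, 0.2 v 0.5 with d = 0.5: Cov = 0.15. Var(G) = (0.32 + 0.50)/2 + 0.09 = 0.50. Bias = 0.5 × 0.15/0.50 = 0.15 SD per allele. r² = 0.0225/0.125 = 0.18. Residual variance = 1 + 0.0625 × 0.82 = 1.051. SE = √(1.051/20) = 0.229. λ = 0.65. Type I error ≈ 0.096 + 0.004 = 0.10.

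The formula uses a normal approximation and leaves out the three covariates. Simulation (3,000 to 20,000 replicates per scenario, least squares) covers the t distribution and, in most runs, three independent covariates standing in for age, gender and BMI.

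| Frequencies | d | Bias (SD per allele) | λ | Formula | Simulated | Simulated with ancestry term |
|---|---|---|---|---|---|---|
| 0.2 v 0.4 | 0.5 | 0.11 | 0.46 | 0.075 | 0.07 | 0.05 |
| 0.2 v 0.5 | 0.5 | 0.15 | 0.65 | 0.10 | 0.09 | 0.05 |
| 0.2 v 0.5 | 0.8 | 0.24 | 1.01 | 0.17 | 0.16 | 0.05 |
| 0.1 v 0.6 | 0.8 | 0.34 | 1.59 | 0.36 | 0.32 to 0.34 | 0.05 |
| 0.3 v 0.3 | 0.8 | 0 | 0 | 0.05 | 0.05 | 0.05 |

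Inflation needs both gaps. With equal frequencies, or with d = 0, the rate stays near 0.05. If ancestry also changes the slope on an exposure that the direct model leaves out, the extra residual variance lowers the third and fourth rows to about 0.13 and 0.25.

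**Moderator test (gene × exposure), by simulation.** The scenarios are 0.2 v 0.5 with 0.5 SD, 0.2 v 0.5 with 0.8 SD, and 0.1 v 0.6 with 0.8 SD.
- Ancestry shifts only the mean outcome: 0.04 to 0.05, no inflation.
- Ancestry also changes the exposure slope by the same amount d: 0.09, 0.15 and 0.26.
- As in the second case, with an ancestry main effect added: 0.10, 0.16 and 0.28, no improvement.
- As in the second case, with ancestry and ancestry × exposure added: about 0.05.

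**The case against.** The strongest objection is that the only Aim 3 model written out in section 12.4 is the moderator analysis, and a shift in mean outcome between ancestry groups does not inflate it. This stands. A reader might take the 16% or 32% to 34% as the error rate of the planned test. The documents do not support that, because those rates belong to the direct associations named as an aim in sections 2 and 3. For the moderator test a second assumption is needed, namely a slope that differs by ancestry.

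A reader might also infer from section 8.6 that race and ethnicity go unrecorded. The wording there introduces examples, not a closed list, and the Schedule of Activities is a separate file that is not among the documents. What can be said is that no ancestry variable is named as collected or as adjusted for. Collecting one would not put it in the model.

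Three further points have some force:
- The sizes are all assumed, and the mildest mixed-ancestry scenario shown (7%) is close to nominal.
- Section 12.4 speaks of targeted genotyping and section 8.4 does not give the array content, so ancestry components may not be obtainable.
- Section 12.2 says that the study is underpowered and that results are pilot data, and section 4 calls the genetic work secondary. This limits the consequence but does not remove the bias.

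The promise in section 10.3 to consider relevant data is made about concomitant therapy. It names neither ancestry nor a model.

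**Conclusion.** The point holds, at low severity. Under the stated covariate rule, Aim 3 does not control for ancestry in a sample whose ancestry is not restricted, and randomization does not protect the comparison. Direct GNAI2 associations are open to confounding. Under the assumed mixes their type I error runs from about 7% to 32% to 34%, against about 5% with an ancestry term measured without error. The moderator test is exposed only if ancestry alters the metabolite-BP or sodium-BP slope.

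The documents do not show that the sample is ancestrally mixed, that GNAI2 allele frequencies differ within it, or that any Aim 3 result will be false. The finding is an uncontrolled path, not a demonstrated bias, and no confirmatory conclusion depends on it.

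**What to change.** In section 12.4, under Specific Aim 3:
1. Add ancestry to age, gender and BMI: one or two principal components from the array if its content allows, otherwise self-reported race and ethnicity. Confirm that race and ethnicity are collected at baseline, and name them in section 8.6.
2. In the moderator models add ancestry × exposure terms as well, at least as a sensitivity analysis. An ancestry main effect alone does not protect the interaction test.
3. State that Aim 3 is exploratory and report it so.

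The cost is at most one questionnaire item plus degrees of freedom. With one SNP coded additively and all 40 people analysed, a direct model has 40 − 5 = 35 residual degrees of freedom, or 33 with two components. A moderator model has 40 − 7 = 33, or 29 with two components and their two interactions. Some precision is lost in a small sample, which is a reason to use one component where one is enough.
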